Official Title of the study: **Effect of Varied Outreach Methods on Appointment Scheduling, Appointment Completion, and Receipt of MMR Vaccination**

NCT number: **NCT04567342**

Document name: **Statistical Analysis Plan**

Date of the document: **7/31/2023**

The results of the Outreach Methods study will be assessed as described in this document. This statistical analysis plan begins with an overview of the key components of the study, including its design, objectives, and outcomes measures. This is followed by a detailed description of the statistical analyses that will be utilized to address study hypotheses.

1. Overview of study: This study used a 2x2 factorial randomized control trial to test the impact of automated text/telephone messages and personal contact attempts on well child care (WCC) scheduling and completion and receipt of MMR vaccine. We randomized eligible patients to 1 of 4 groups: 1 automated message (Group 1), 2 automated messages (Group 2), 1 automated message plus personal contact attempts (Group 3), or 2 automated messages plus personal contact attempts (Group 4). We generated random allocation sequence stratified by clinic location using block randomization (with a block size of 4). Based on sample size calculations, we planned to enroll a minimum of 668 subjects overall aged 12-14 months old and 4 years old that met eligibility criteria based on data obtained from the electronic health record (EHR) from three academic pediatric primary care practices.

1.1 Study Objective: Test the effectiveness of text/telephone outreach messages and personal contact attempts on well child care (WCC) scheduling and completion and receipt of MMR vaccine.

Working hypothesis: Twenty percent of patients in Group 1, 35% of patients in Group 2, and 50% of those in Group 3, and 65% of those in Group 4 would receive the MMR vaccine by 15 months of age (for children who were 12-14 months old) or receipt of the second MMR dose by 3 months after first intervention (for children 4 years old).

1.2 Outcome measures

Primary

- Receipt of MMR by 15 months of age (for children who were 12-14 months old) or receipt of the second MMR dose by 3 months after first intervention (for children 4 years old).
 - Receipt of MMR (yes or no) based on electronic health record documentation

Secondary

- Well-child visit scheduled within 2 weeks of receiving first intervention
 - Appointment scheduled (yes or no) based on electronic health record documentation
- Well-child visit completed within 8 weeks of receiving first intervention
 - Appointment completed (yes or no) based on electronic health record documentation

1.3 Time points of interest

- Receipt of MMR (by 15 months of age or by 3 months after first intervention for children 4 years old)
- Scheduled well-child visit (within 2 weeks of receiving first intervention)
- Completed well-child visit (within 8 weeks of receiving first intervention)

1.4 Data Management

CCHMC CRC will guide data management for this project as described in the study protocol.

1.5 Interim Safety Analyses

No interim analyses are planned for this study.

2. Statistical Reports

2.1 Report Generation

2.1.1 Software

Outreach Methods SAP

Version 1.1, 7/31/23

pg. 1

All statistical analyses will be performed using SAS version 9.4 (SAS Institute Inc., Cary, NC, USA) under Microsoft Windows operating system

2.2 Analysis Populations

2.2.1 Completion

Subjects will be considered to have completed the study on the study end date on 8/6/21.

2.2.2 Missing data

We will use data obtained from patient's electronic health record (EHR) to calculate our primary and secondary outcomes. Missing outcome data could occur for several reasons, such as errors of medical documentation or the patient no longer in the primary care registry.

2.3 Statistical Report Contents

The following section outlines the contents of the final statistical analysis. For all analyses, subjects who are enrolled in the study and are eligible will be analyzed in the groups to which they were allocated.

2.3.1 Description of study population

Sample size:

The total number of subjects who are enrolled will be given.

Demographics and Clinical Characteristics, Patient and Parent:

Demographic and clinical characteristics as measured at baseline will be summarized by trial arm. Variables to be summarized are: child age, child sex, child race, child ethnicity, insurance, parent communication preference absence of past patient receipt of tetanus and acellular pertussis (DTaP) vaccine as a proxy for childhood vaccine refusal, and patient lifetime historical institutional no-show rate. Variables will be summarized using descriptive statistics appropriate for each type of data item.

Baseline characteristics with large differences between groups will be included in analyses as covariates.

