1 personal contact attempt	Above plus attempt Mon – Fri of following week (weeks 2, 7, 11)	Above plus attempt Mon – Fri of following week (weeks 1, 8, 9)

MyChart and Televox Trials (6-17 years old):

Randomization: Eligible patients will be identified by running a report in the electronic health record (EHR). We will run this report, stratified by clinic location, and randomly assign patients into one of the study groups as described above. Groups will receive their assigned intervention in one of four successive weeks with the sequence randomly assigned (see table below).

We will randomize children who are eligible and implement interventions for each trial : Weeks 1-3 = Televox Trial 12-17yo, Weeks 4-7 = Televox Trial 6-11yo, Weeks 8-10 = MyChart Trial.

MyChart Trial:

	no message	1 MyChart message sent	2 MyChart messages (e.g. Mon and Thurs)
Standard Message	No intervention	Week A	Week B
Tailored Message		Week A	Week B

Televox (6-11yo) Trial:

no message	Low Tailored Message 2 automated standard messages sent (e.g. Thu, Fri) (weeks C, C)	High Tailored Message 2 automated tailored messages sent (e.g. Thu, Fri) (weeks D, D)
-------------------	---	--

Televox (12-17yo) Trial:

no message	Low Tailored Message 2 automated tailored messages sent (e.g. Thu, Fri) (week A)	COVID Tailored Message 2 automated messages sent (e.g. Thu, Fri) (week B)
-------------------	---	--

Of note, automated messages and/or personal contact attempts will not be completed if the parent schedules an appointment after being randomized but before receiving the intervention.

Covariates for logistic regression: (factors that might influence the outcome if not be balanced across groups)

1. Child age at the time of randomization (rationale: visits are less frequent for children age 4 years)
2. Parent preference for call vs. text mode of contact (rationale: calls may be more likely to get blocked than texts)
3. Parent with activated MyChart account (Y/N) (rationale: not dependent on calling scheduling center to make appointment)
4. Access to appointment: Number of days to 3rd next available appointment at patient's clinic at time their first automated message is sent
5. Patient receipt of any past immunizations (Y/N) (rationale: vaccine refusing parents will be unlikely to change even if they return for well child check)

6. School-age vs. adolescent patient age (rationale: adolescents less likely to get yearly check-ups)
7. Historical no-show rate

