8. Community rates of COVID based on 7 day moving average.

Power/Sample Size

Personal Contacts (12-14 month & 4-year-olds) Trial:

We based our hypotheses (see table, below) on a systematic review's pooled estimates of effect size for automated messages and personalized calls finding 37% and 40% of children, respectively, completed immunizations.¹ Because of the significant cost involved in making personal contacts, the minimal difference in outcome that would make it worth the effort is high.

Hypotheses	% of children who receive MMR by 15 months of age	
	1 automated message sent	2 automated messages sent
0 personal attempts	20% ^C	35% ^B
1 personal attempt	50% ^A	65% ^{AB}

We calculated sample size needed per group to detect a difference for each of the contrasts below with alpha of 0.05 and power of 80%.

Contrast	Sample Size per Group
A vs C	36
B vs C	136
A vs. B	167
A vs. AB	167
B vs. AB	40
C vs. AB	16

To fully power the 2 X 2 factorial trial, we estimate needing 167 per group X 4 groups = 668 total subjects. There are currently 712 children eligible for the study. More will become eligible every month so we expect to far exceed the required sample size after 3 replications. If needed, we could increase the number of replications of the trial to reach the targeted sample size. We acknowledge that we are not powered to precisely estimate any interactions between interventions.

MyChart Trial:

In hypothesis testing for 0 message vs. 1 message vs. 2 messages, we will do the testing in a fixed sequence - test 2 messages vs. 0 message first, only if it is significant then test 2 messages vs. 1 message, thus the type I error rate of 0.05 is retained. Since the hypothesis testing of 2 messages vs. 0 message would be considered easier to achieve than the hypothesis testing of 2 messages vs. 1 message, the power analysis for this trial should be based on the design of (standard message vs. tailored message) by (1 message vs. 2 messages). We based our hypotheses (see table, below) on previous work indicating approximately 20% WCC appointment completion on automated text reminders. We anticipate that a tailored message increases the WCC appointment completion rate by another 10%.

Hypotheses		% of children complete WCC within 8 weeks	
		1 automated message sent	2 automated messages sent
Standard Message	2%	10% ^C	20% ^B
Tailored Message		20% ^A	30% ^{AB}

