We calculated sample size needed per group to detect a difference for each of the contrasts below with alpha of 0.05 and power of 80%.

Contrast	Sample Size per Group
A vs C	199
B vs C	199
A vs. AB	293
B vs. AB	293
C vs. AB	62

We assume no difference between A vs. B and thus not consider powering the comparison between these two groups, but we will explore non-inferiority analysis for this comparison in data analysis. To fully power the above contrasts, we estimate needing 293 per group X 4 groups = 1172 subjects. Adding 293 in the zero message group, we would need a total of 1465 subjects. There are currently 1000 children eligible for the study. More will become eligible every month so we expect to exceed the required sample size after 2 replications. If needed, we could increase the number of replications of this trial to reach the targeted sample size. We acknowledge that we are not powered to precisely estimate any interactions between interventions.

Televox (6-11yo) Trial:

We calculated sample size based on the following hypotheses:

% of children complete WCC within 8 weeks		
no message	2 Low Tailored Messages	2 High Tailored Messages
2%	20%	30%

With alpha of 0.05 and power of 80%, to fully power the contrasts between the above groups, we need 293 per group X 3 groups=879 subjects. Currently there are 2500 kids eligible, so we expect to reach the targeted sample size.

Televox (12-17yo) Trial:

We calculated sample size based on the following hypotheses:

% of children complete WCC within 8 weeks		
no message	2 Low Tailored Messages	2 COVID Tailored Messages
2%	30%	40%

With alpha of 0.05 and power of 80%, to fully power the contrasts between the above groups, we need 356 per group X 3 groups=1068 subjects. Currently there are 1100 kids eligible, so we expect to reach the targeted sample size.

Analysis

We will conduct descriptive analyses to characterize the participants in terms of demographics and other potential covariates in consideration (child age group, parent's preference for call vs. text mode of contact, whether parent had activated MyChart account, access to appointment, whether patient receipt of any past immunizations, historic no show rate, and community rates of COVID). We will use chi square tests to examine whether participants in the 4 groups are similar in these characteristics.

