For the Personal Contact (12-14 mo & 4 years old) trials, we will conduct intent-to-treat analyses using logistic regression models (without adjusting for covariates) for each of our three binary outcomes: completed appointment

within 2 weeks, completed appointment within 8 weeks, receipt of MMR by 15 months of age or receipt of 2nd MMR by 3 months after randomization. We will do pair-wise comparison among the 4 groups and adjust p value of each comparison for multiplicity. If participants in the 4 groups differ on potential covariates, we will conduct additional analyses adjusted for these variables.

For the MyChart and Televox Trials (6-17 years old), we will conduct intent-to-treat analyses using logistic regression models (without adjusting for covariates) for each of the binary outcomes: scheduled appointment within 2 weeks, completed appointment within 8 weeks, receipt of 1st dose of COVID vaccination (age 12-17 years) within 8 weeks, family member receipt of COVID vaccination within 8 weeks. We will do pair-wise comparison among the treatment groups and adjust p value of each comparison for multiplicity. If participants differ in potential covariates across treatment groups, we will conduct additional analyses adjusted for these variables. We will explore non-inferiority analysis for comparison the two groups that are expected to have similar appointment scheduled and completion rate in the MyChart trial.

We will also conduct per-protocol analyses according to the interventions actually received by the participants, recognizing that actual intervention received could be different from initial randomized intervention. For example, a parent allocated to group A might schedule an appointment after receiving the automated message and therefore would not receive a personalized contact attempt. In addition, we may explore potential interaction between the two interventions as a secondary analysis. All analysis will be conducted using SAS version 9.4.

Duration

The study will begin upon IRB approval and continue through December 31, 2022. During this time, we will discuss the significance of data, potential future projects and dissemination of results.

Process of Obtaining Consent

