2.3.2 Primary outcome analysis

Primary outcome: Receipt of MMR by 15 months of age (for children who were 12-14 months old) or receipt of the second MMR dose by 3 months after first intervention (for children 4 years old).

- Receipt of MMR (yes or no) based on electronic health record documentation

For the primary outcome, we will use a modified Poisson regression models to estimate risk ratio (RRs) with statistical significance defined as 2-sided $p < .05$. If participants differ in potential covariates across treatment groups, we will conduct additional analyses adjusted for these variables.

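### Covariates enter the models only when the arms look different at baseline, so predictors the plan expects to matter are usually left out, and one SAP sentence conflicts with the rest of the plan on whether adjustment is additional

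*SAP*

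**What the plan says.** **Entry rule.** SAP section 2.3.1, which describes the study population, says: "Baseline characteristics with large differences between groups will be included in analyses as covariates". SAP section 2.3.2 says: "If participants differ in potential covariates across treatment groups, we will conduct additional analyses adjusted for these variables", and section 2.3.3 repeats this for both secondary outcomes. The protocol's Analysis section has the same trigger ("If participants in the 4 groups differ on potential covariates, we will conduct additional analyses adjusted for these variables") and supplies a test for it: "We will use chi square tests to examine whether participants in the 4 groups are similar in these characteristics". No significance level or size of difference is given.

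**Main model.** For the Personal Contacts trial the protocol plans "intent-to-treat analyses using logistic regression models (without adjusting for covariates". SAP section 2.3.2 changes the model without saying whether it is adjusted: "we will use a modified Poisson regression models to estimate risk ratio (RRs) with statistical significance defined as" a two-sided p below .05.

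**Candidate covariates.** SAP section 2.3.1 lists eight baseline variables: age, sex, race, ethnicity, insurance, communication preference, absence of past DTaP (as a proxy for vaccine refusal) and lifetime no-show rate. The protocol's Analysis section lists seven. Contact mode, past immunization and no-show rate are common in substance to both. The protocol explains past immunization by saying that "vaccine refusing parents will be unlikely to change even if they return for well child check".

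**Time-dated covariates.** The protocol's covariate list, but not the SAP's, has "Community rates of COVID based on 7 day moving average", with no measurement date. It also has days to the third next available appointment, taken when the first automated message goes out.

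**The concern.** In a randomized trial a baseline difference between arms is a chance event. It does not show which variables predict the outcome, and that is what decides whether adjustment helps. A rule that waits for imbalance will usually omit a strong predictor and will sometimes admit an irrelevant one. With no threshold, the analyst decides what counts as a large difference after seeing the baseline table.

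Two things are at stake. The first is precision from variables the plan already intends to collect. The second is clarity about which risk ratio is the main result, because the sentence in SAP section 2.3.1 puts flagged variables into the analyses while the other passages make adjusted models additional. In the MyChart and Televox trials, for which the protocol is the only analysis plan, the candidate list also includes variables that may be fixed by the week in which an arm was messaged.

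**Working it through.** **1. The plan's own figure.** Inputs are the assumed MMR rates of 20%, 35%, 50% and 65%, alpha 0.05 (two-sided) and power 80% (protocol, Power/Sample Size). The unpooled two-proportion formula for the largest contrasts, for example 50% vs 35%, gives

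n = (1.960 + 0.842)² × [0.50×0.50 + 0.35×0.65] / 0.15² = 7.85 × 0.4775 / 0.0225 = 166.6, so 167 per group and 4 × 167 = 668.

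The same formula reproduces all six contrasts (36, 136, 167, 167, 40, 16). No covariate enters it, so the planned size does not depend on adjustment.

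**2. How often the trigger fires by chance.** Assume independent screens at 5% (the documents give no level):

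- A given predictor is flagged 5% of the time and left out 95% of the time.
- At least one flag among the SAP's eight variables: 1 − 0.95⁸ = 0.337.
- Among the protocol's seven: 1 − 0.95⁷ = 0.302.
- Among five, setting aside COVID rate and appointment access because they may be tied to delivery date: 1 − 0.95⁵ = 0.226.

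**3. What the rule costs.** The check was a simulation of 35% vs 50% with 167 per group and one binary predictor of assumed prevalence 20%. It used 6,000 runs per scenario and a linear model with robust standard errors (a stand-in for modified Poisson). The predictor's risk ratio for the outcome was varied.

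| Predictor's RR | Unadjusted | Adjusted only if imbalanced | Always adjusted | Gain, always vs unadjusted |
|---|---|---|---|---|
| 0.2 | 79.6% | 80.1% | 83.8% | 4.2 points |
| 0.5 | 79.3% | 79.4% | 80.6% | 1.3 points |
| 1 (not predictive) | 79.9% | 79.9% | 79.7% | −0.2 points |

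The simulation error of each power is about √(0.8×0.2/6000) = 0.5 points. The imbalance rule recovers almost none of the gain. With no treatment effect, rejection rates were 5.0% to 5.6% across all three approaches.

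**4. Which estimate is primary.** The protocol's Analysis section calls its main model unadjusted. That section and SAP sections 2.3.2 and 2.3.3 call adjusted models additional. Only the sentence in SAP section 2.3.1 puts flagged variables into the analyses without that qualifier. SAP section 2.3.2 does not restate that its new model is unadjusted.

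**5. Covariates dated to delivery.** In the protocol's Televox 12–17 schedule, the low tailored arm is messaged in week A and the COVID tailored arm in week B.

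- If there is one community rate per week, dated to delivery, every child in a message arm has the same value. In a single run the rate is then collinear with arm.
- The no-message arm has no delivery date at all.
- If the rate is dated to randomization, it is identical for every child in the run and adjusts nothing.
- Days to the third next available appointment is set by clinic and delivery date, so within a clinic it follows the arm's week.

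**The case against.** The strongest reply is that the plan does name its main analysis. The protocol says unadjusted, and every passage on the models themselves calls adjustment additional. The SAP 2.3.1 sentence sits in a descriptive section and can be read as saying which variables enter those additional models. This stands: a reader might infer that the primary estimate is undecided, but the documents show an inconsistency with one sentence.

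A reader might also infer inflated type I error. The simulation shows none, and a flag leads at most to an additional analysis on most readings.

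A third tempting reading is that the COVID rate spoils the adjusted models throughout. It is not in the SAP's list, so the SAP rule cannot bring it in, and it has no stated date. In Personal Contacts each arm is sent in three different weeks. With simulated weekly rates dated to delivery, arm explained a median of only 11% to 25% of the rate's variance, so arm effects remain estimable. MyChart has 1000 eligible children against 1465 needed and expects two replications, so full collinearity does not follow there either.

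Finally, the SAP is dated 7/31/2023 and gives a study end date of 8/6/21. Making an adjusted model primary now would itself be a late choice. That is fair and shapes the fix. The dates do not show that anyone chose covariates after seeing results.

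**Conclusion.** The point holds in limited form. Covariate entry depends on chance imbalance with no threshold, so predictors that the plan collects and expects to matter are usually left out. The wording of SAP section 2.3.1 conflicts with SAP section 2.3.2 and the protocol.

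The loss is modest, about 0 to 4 power points, and rests on assumptions that the documents do not supply: a 5% screen, 20% prevalence and the predictor strengths in the table. The 23% to 34% chance of at least one flag also assumes independent screens. The sample size of 668 stands.

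The collinearity problem is confined to adjusted analyses of a single-run trial such as Televox 12–17, and only if a week-level rate is dated to delivery. It is worth correcting, but it does not undermine the trial.

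**What to change.** - Replace the imbalance trigger in SAP sections 2.3.1 to 2.3.3 and the protocol's Analysis section with one fixed list, used whatever the baseline table shows: no-show rate (continuous), the DTaP or past-immunization proxy, and contact mode. Clinic and age-group terms are a separate matter.
- Name one estimate as primary and the other as sensitivity. The precision gain reaches the primary result only if the adjusted estimate is the one named. If the protocol's unadjusted estimate is kept, the fixed list should still define the adjusted one.
- Align SAP section 2.3.1 with section 2.3.2 and the protocol, and state in 2.3.2 whether the modified Poisson model is adjusted.
- Drop the baseline chi-square tests as a selection device and keep the descriptive table.
- Date and justify the change, given the SAP date, and always report the unadjusted risk ratio.
- For MyChart and Televox, do not adjust for covariates dated to message delivery: community COVID rate if so dated, and days to the third next available appointment. Report both by week as description.

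The cost is wording in the two documents. The three covariates are already among those the SAP plans to summarize, and no more children are needed.
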